1.1 Study design

This is a multicenter, participant and investigator-blinded, randomized, placebo-controlled study to characterize PK/PD profile and to evaluate the safety and the efficacy of TIN816 in hospitalized adult participants with diagnosis of sepsis and acute kidney injury (AKI). Approximately 20 participants will be randomized in the study. The study consists of a screening period (up to 48 hours), treatment period (Day 1), and post-treatment period (Day 2 to 90) and is summarized in [Figure 1-1](#).

An interim analysis (IA) is planned when approximately 8 participants complete Day 14 visit. The study will continue without modification if a similar PK profile of TIN816 compared to the one in the healthy volunteers (HV) is confirmed. Otherwise, an adaptive design would be implemented with options to add up to two additional arms testing a higher dose, multiple bolus doses, extended infusion dosing regimens or combination of bolus dose and extended infusion.

The adaptive design will be supported by modeling and simulation with data from the preclinical studies, first in human (FIH) study and the IA of the current PK/PD study. Patient recruitment will continue during the IA to enroll up to a cap of 12 patients. In the circumstance that the first IA does not provide sufficient PK data to support phase 2b, an additional IA will be added when all 20 patients complete Day 14 visit.

Figure 1-1 Study design

^A interim analysis (IA) based on 8 patients with 14-day data collected from baseline

^B conditional additional interim analysis (IA) based on 20 patients with 14-day data collected from baseline

* participant-investigator blinded

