The term **“unscheduled visit”** refers to visits that occurred not as part of the Clinical Trial Protocol assessment schedule. Data collected at unscheduled visits will, in general, not be used in ‘by-visit tabulations’ or graphs, but they will be included in analyses of safety parameters based on all post-baseline values such as summary statistics of clinically notable abnormalities of laboratory data. For efficacy evaluations, measurements from unscheduled visits will generally not be used, unless where otherwise specified. All data collected at both scheduled and unscheduled visits will be included in data listings.

“Completion”: a participant will be considered to have completed the study when the patient has completed the Day 90 visit in the study or End of Study (EOS) for participants who discontinue from the study. The maximum of the date of last visit in the randomized treatment period, date of withdrawal of consent (in case of withdrawal from study), would be the date of **last contact** for the patient in the study.

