5.1 Imputation rules

5.1.1 AE date imputation

AE end date imputation

Rules for imputing AE end dates are stated below. Date of last contact in the study has been defined as in [Section 2.1.1](#).

1. If the AE end date month is missing, the imputed end date should be set to the earliest of the (date of last contact, 31DECYYYY, date of death).
2. If the AE end date day is missing, the imputed end date should be set to the earliest of the (date of last contact, last day of the month, date of death).
3. If AE year is missing or AE is ongoing, the end date will not be imputed.

AE start date imputation

Rules for imputing the AE start date:

The following table explains the notation used in the logic matrix. Please note that **missing start dates** will not be imputed.

	Day	Month	Year
Partial Adverse Event Start Date	Not used	MON	YYYY
Treatment Start Date	Not used	TRTM	TRTY

The following matrix explains the logic behind the imputation.

	MON MISSING	MON < TRTM	MON = TRTM	MON > TRTM
YYYY MISSING	(1) No convention			
YYYY < TRTY	(2.a) Before Treatment Start	(2.b) Before Treatment Start	(2.b) Before Treatment Start	(2.b) Before Treatment Start
YYYY = TRTY	(4.a) Uncertain	(4.b) Before Treatment Start	(4.c) Uncertain	(4.c) After Treatment Start

YYYY > TRTY	(3.a) After Treatment Start	(3.b) After Treatment Start	(3.b) After Treatment Start	(3.b) After Treatment Start
-------------	-------------------------------------	-------------------------------------	-------------------------------------	-------------------------------------

Before imputing AE start date, find the AE start reference date.

1. If the imputed AE end date is complete and the imputed AE end date < treatment start date then AE start reference date = min(informed consent date, earliest visit date).
2. Else AE start reference date = treatment start date

Impute AE start date -

1. If the AE start date year value is missing, the date uncertainty is too high to impute a rational date. Therefore, if the AE year value is missing, the imputed AE start date is set to NULL.
2. If the AE start date year value is less than the treatment start date year value, the AE started before treatment. Therefore:
 - a. If AE month is missing, the imputed AE start date is set to the mid-year point (01JulYYYY).
 - b. Else if AE month is not missing, the imputed AE start date is set to the mid-month point (15MONYYYY).

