3. If the AE start date year value is greater than the treatment start date year value, the AE started after treatment. Therefore:
 - a. If the AE month is missing, the imputed AE start date is set to the year start point (01JanYYYY).
 - b. Else if the AE month is not missing, the imputed AE start date is set to the later of (month start point (01MONYYYY), AE start reference date + 1 day).
4. If the AE start date year value is equal to the treatment start date year value:
 - a. And the AE month is missing the imputed AE start date is set to the AE reference start date + 1 day.
 - b. Else if the AE month is less than the treatment start month, the imputed AE start date is set to the mid-month point (15MONYYYY).
 - c. Else if the AE month is equal to the treatment start date month or greater than the treatment start date month, the imputed AE start date is set to the later of (month start point (01MONYYYY), AE start reference date + 1 day).

If complete imputed AE end date is available and the imputed AE start date is greater than the imputed AE end date, then imputed AE start date should be set to the imputed AE end date.

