5.1.2 Concomitant medication date imputation

Concomitant medication end date imputation

Rules for imputing the CM end date are stated below. Date of last contact in the study has been defined as in [Section 2.1.1](#). Concomitant medication end dates will not be imputed for ongoing records.

1. If CM end day is missing and CM month/year are non-missing then impute CM day as the minimum of date of last contact and the last day of the month.
2. If CM end day/month are missing and CM year is non-missing then impute CM day as the minimum of date of last contact and the end of the year (31DECYYYY).
3. If CM day/month/year is missing then use the date of last contact + 1 day as the imputed CM end date.
4. If imputed CM end date is less than the CM start date, use the CM start date as the imputed CM end date.

Concomitant medication start date imputation

Rules for imputing the CM start date:

The following table explains the notation used in the logic matrix. Please note that **missing start dates** will not be imputed.

	Day	Month	Year
Partial CMD Start Date	Not used	MON	YYYY
Treatment Start Date	Not used	TRTM	TRTY

The following matrix explains the logic behind the imputation.

	MON MISSING	MON < TRTM	MON = TRTM	MON > TRTM
YYYY MISSING	(1) Uncertain	(1) Uncertain	(1) Uncertain	(1) Uncertain
YYYY < TRTY	(2.a) Before Treatment Start	(2.b) Before Treatment Start	(2.b) Before Treatment Start	(2.b) Before Treatment Start
YYYY = TRTY	(4.a) Uncertain	(4.b) Before Treatment Start	(4.a) Uncertain	(4.c) After Treatment Start
YYYY > TRTY	(3.a) After Treatment Start	(3.b) After Treatment Start	(3.b) After Treatment Start	(3.b) After Treatment Start

1. If the CM start date year value is missing, the imputed CM start date is set to one day prior to treatment start date.
2. If the CM start date year value is less than the treatment start date year value, the CM started before treatment. Therefore:
 - a. If the CM month is missing, the imputed CM start date is set to the mid-year point (01JulYYYY).
 - b. Else if the CM month is not missing, the imputed CM start date is set to the mid-month point (15MONYYYY).
3. If the CM start date year value is greater than the treatment start date year value, the CM started after treatment. Therefore:
 - c. If the CM month is missing, the imputed CM start date is set to the year start point (01JanYYYY).

- d. Else if the CM month is not missing, the imputed CM start date is set to the month start point (01MONYYYY).

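### Read literally, the SAP's date of last contact is Day 1, so partial end dates for adverse events and some medications, and some adverse event start dates, could be imputed to the dosing day

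*SAP*

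**What the plan says.** SAP 2.1.1, in the paragraph on completion, defines the date of last contact by "The maximum of the date of last visit in the randomized treatment period, date of withdrawal of consent". The term *randomized treatment period* is not explained anywhere. SAP 1.1 divides the study after screening into a "treatment period (Day 1), and post-treatment period (Day 2 to 90". Protocol 1.1 makes the same split, and Protocol Table 1-2 places every visit from Day 2 to Day 90 under post-treatment.

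The imputation rules take the definition over by cross-reference: "Date of last contact in the study has been defined as in" Section 2.1.1. The rules that use it are these:

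- AE end date, day missing: "earliest of the (date of last contact, last day of the month, date of death".
- AE end date, month missing: "earliest of the (date of last contact, 31DECYYYY, date of death".
- AE start date, closing rule: if the imputed start is later than the imputed end, "then imputed AE start date should be set to the imputed AE end date".
- Medication end date, partial: the earlier of last contact and the end of the month or year (SAP 5.1.2, rules 1 and 2).
- Medication end date, wholly missing: "If CM day/month/year is missing then use the date of last contact + 1 day as the imputed CM end date".
- Medication floor (SAP 5.1.2, rule 4): an imputed end date that precedes the medication's start is replaced by the start date.

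Ongoing AEs, AEs with no end year and ongoing medications get no imputed end date.

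**The concern.** A last-contact date is meant to be the outer limit of follow-up, so that no imputed end date runs past the point where the participant was last observed. If that limit sits on the dosing day, the earliest-of rule no longer trims a few late dates. It pulls back every partial AE end date that falls after dosing.

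Two consequences matter for the safety tables and listings. First, SAP 5.1.1 has no floor for AE end dates, so an event can be given an end before its own recorded start. Second, the start-date rules place an uncertain post-dose onset no earlier than the day after the reference date, which is normally Day 2. That keeps the event after dosing. A Day 1 end date combined with the closing rule undoes this protection. SAP 2.6.1 counts an event as treatment-emergent if it started after the first dose, so an event reset to Day 1 could drop out if dates are compared without times.

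**Working it through.** The plan states no figure to reproduce. The check applies the SAP 5.1 rules to one illustrative participant.

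**Inputs.** Assumption: dosed on 10 March, so Day 90 is 7 June of the same year. April then runs from Day 23 to Day 52. No death, and medication start dates are known.

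**Formulas.**
- Last contact = max(last visit in the treatment period, date of consent withdrawal). With the treatment period equal to Day 1 and no withdrawal, this is Day 1.
- AE end = min(last contact, month or year end, death).
- AE start (month equal to or after the dosing month, same year) = max(first of the month, reference date + 1 day), then capped at the imputed AE end. An imputed end on Day 1 is not before dosing, so the reference date stays at Day 1.
- Medication end = min(last contact, month or year end), or last contact + 1 day if wholly missing, and never before the medication's start.

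**Results.**

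| Record | Last contact = Day 1 (literal) | Last contact = Day 90 visit | Shift (days) |
|---|---|---|---|
| AE end, April | Day 1 | Day 52 | 51 |
| AE end, year only | Day 1 | Day 90 | 89 |
| AE start, when start and end are both April | Day 1 | Day 23 | 22 |
| AE start, when start and end are both March | Day 1 | Day 2 | 1 |
| AE end, April, with known start on Day 25 | Day 1 | Day 52 | 51 |
| Medication started before dosing, end April | Day 1 | Day 52 | 51 |
| Medication started on Day 20, end April | Day 20 | Day 52 | 32 |
| Medication started before dosing, end wholly missing | Day 2 | Day 91 | 89 |

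In the fifth row the event ends 25 − 1 = 24 days before it began.

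**What does not move.** An AE starting in April with a complete end date of 20 April, or ongoing, keeps its imputed start on Day 23 under either definition. If consent is withdrawn on Day 40, the maximum picks Day 40: the April AE end becomes Day 40 and the April AE start stays at Day 23. A wholly missing, non-ongoing medication end goes to Day 2 only if the medication started by Day 2; otherwise rule 4 gives its own start date.

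**Evidence of intent.** The same paragraph of SAP 2.1.1 ties completion to the Day 90 visit or end of study. SAP 2.4.1 computes study duration from the last visit with no restriction to a period. SAP 2.6.1 counts AEs over the 90-day study period. All three point to the last study visit.

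**The case against.** The strongest reply is that nobody would program it this way. The period named in the definition is undefined, equating it with Day 1 is an inference, and the surrounding text plainly looks to Day 90. On that view this is loose wording rather than a flawed rule. The effect is also narrow. It needs a partial date with a known year, it needs both AE dates to be partial before a start moves, and Protocol 8.6.1 asks for start and end dates as far as possible. Rule 4 of SAP 5.1.2 protects medications started after dosing.

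Most of this stands, and it sets the limits of the point. The effect is conditional on the literal reading, and that reading is probably not the intended one. It does not remove the point. The SAP is the programming specification, the only treatment period it defines is Day 1, and a programmer who follows the cross-reference as written gets wrong dates.

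Two stronger readings are tempting. A reader might infer that an event moved to Day 1 would be classed as an infusion or hypersensitivity reaction. The documents do not support that: SAP 2.6.1 summarises events of special interest by type, no rule assigns the type from an imputed date, and the SAP does not say that listings will show imputed rather than recorded dates. A reader might also express one shifted event as a share of the small placebo arm. No planned table in the public text counts events by onset on Day 1, so that percentage would correspond to no output. The one visible route to a planned AE table is loss of treatment-emergent status.

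**Conclusion.** The point holds as a conditional defect of minor weight. Taken literally, SAP 2.1.1 sets last contact to Day 1 for every participant who does not withdraw consent. The consequences are then:

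- Partial AE end dates after dosing, with a known year and the AE not ongoing, become Day 1, even before a known start.
- When start and end are both partial, an imputed post-dose start also becomes Day 1. On a date-only comparison the event could then lose its treatment-emergent status; if times are used, or Day 1 onsets are accepted, it need not.
- Partial medication end dates become Day 1 only for medications started by Day 1. Wholly missing, non-ongoing end dates become Day 2 only for those started by Day 2. Later-started medications get their own start date. Because SAP 2.4.2 counts any medication ending on or after Day 1 as concomitant, these shifts affect apparent duration and not concomitant status.

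The largest shift is 90 − 1 = 89 days, assuming a last visit on Day 90. The number of affected records cannot be known from the documents. The primary pharmacokinetic endpoint is untouched.

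**What to change.** In SAP 2.1.1, replace the last visit in the randomized treatment period with the last attended visit or documented contact in the study, through Day 90 or end of study. Keep the maximum with the date of consent withdrawal. In SAP 5.1.1, add that an imputed AE end date may not precede a known AE start date, to match the floor that SAP 5.1.2 already gives medications. The other imputation rules can stay as they are.

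The cost is a changed phrase and one added sentence. No new data are needed. If the last study visit was always intended, the new definition changes no intended analysis.

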2.2 Analysis sets

The Screening set (SCR) consists of all patients who have been screened. The purpose of the screening set is to describe the number of patients in screen failures. Screen failures are the patients included in the screening set but not randomized.

The Randomized Analysis Set (RAS) consists of all randomized participants. This analysis set will not be used for any analyses and is solely intended for providing complete information on how participants were randomized.

The PK analysis set will include all participants who receive treatment and survive Day 7 with at least one available valid (i.e., not flagged for exclusion) PK concentration measurement, who received complete study drug regardless of infusion duration. The PD analysis set will include all participants who receive treatment with available PD data. Participants will be analyzed according to actual study treatment received.

The full analysis set (FAS) comprises all participants to whom study treatment has been assigned by randomization. According to the intent to treat principle, participants will be analyzed according to the treatment they have been assigned to during the randomization procedure. Mis-randomized participants, that is, participants who were randomized incorrectly and did not receive any study drug will be excluded from this set. This will be the analysis set used for all efficacy analyses.

The safety set (SAF) includes all participants who received one dose of study treatment. Participants will be analyzed according to the study treatment received, where treatment received is defined as the participant took at least one dose of that study treatment regardless treatment group randomized to. This will be the analysis set used for safety analysis except for PK/PD analysis.

Immunogenicity set includes all subjects in the Safety set with a non-missing baseline anti-drug antibodies (ADA) result or at least one non-missing post-baseline ADA result.

2.3 Patient disposition, demographics and other baseline characteristics

Demographic and other baseline data including disease characteristics will be summarized descriptively for the FAS by treatment group. In addition, summaries of relevant past or current medical conditions will be presented.

Categorical data will be presented as frequencies and percentages. The summary statistics shown for continuous data will be n, mean, standard deviation, median, minimum, and maximum.

2.3.1 Patient disposition

The number of patients screened, screened but not enrolled, completed and discontinued from the study will be summarized. The reasons for screen failure will be provided for the FAS by treatment group. Patients discontinued from the study will also be summarized with reasons for discontinuation. If the disposition is related to COVID-19, the relationship to COVID-19 will also be presented.

The number of subjects with protocol deviations will be tabulated by deviation category as well as deviation related to COVID-19 for the FAS. The number of patients by country will also be presented.

Demographic and baseline characteristics table include but not limited to the following information:

- Informed consent provider (Self/Legal guardian)
- Age
- Sex
- Ethnicity
- Race
- Weight [kg]
- Height [cm]
- Body mass index (BMI) [kg/m²]
- Smoking history
- Alcohol history
- Baseline serum creatinine value (as defined above in [Section 2.1.1](#))

Sepsis diagnosis characteristics at screening visit and APACHE II score at Day 1 include the following information:

- SOFA score ≥ 2 (yes/no)
- Septic shock (yes/no)
- Presumptive source of the infection
- Blood culture performed (yes/no)
 - Positive: Gram positive bacteria, Gram negative bacteria, fungal infection, other
 - Negative
- APACHE II score

AKI diagnosis at screening visit include but not limited to following information:

- Diagnosis of AKI based on KDIGO Serum Creatinine criteria (yes/no)
- Stage of AKI stage based on DKIGO criteria
- Serum creatinine level
- Urine output
- Fluid resuscitation (yes/no)
- Vasopressor (yes/no)
- Renal replacement therapy (yes/no)
- Mechanical ventilation (yes/no)

2.3.2 Relevant Medical History and current medical conditions

Medical history will be coded using the Medical Dictionary for Regulatory Activities (MedDRA) terminology using the most recent version at the time when the last patient has

completed the study. Medical history terms will be summarized by primary system organ class and preferred term.

2.4 Treatments (study treatment, rescue medication, concomitant therapies, compliance)

2.4.1 Study treatment / Treatment of interest

The “treatment of interest” is a single dose of investigational study treatment TIN816 administered via an IV infusion.

The Safety set (SAF) will be used for the analyses below, unless otherwise specified. Descriptive statistics will be provided.

Duration of study period

The “duration of study” will be computed as the time from the date of first study treatment administration to the minimum of the following:

- Date of the last visit
- Date of participant’s death
- Date of participant’s withdrawal of consent

Dose Exposure

The duration of exposure (in hours) to study treatment will be computed and summarized, but excluding temporary treatment interruptions.

Total volume (ml) administered will also be summarized.

2.4.2 Prior, concomitant and post therapies

Analyses in this section will be based on the SAF. Descriptive statistics will be provided.

Prior medications and significant non-drug therapies are defined as any medications and significant non-drug therapies taken at least a day prior to the start of study treatment (Day 1).

Concomitant medications and significant non-drug therapies are defined as those taken at or after the start of study treatment (i.e. with end date on or after Day 1, ongoing at EOS or with missing end date and start date prior to the end of study treatment).

Medications and significant non-drug therapies that started prior and were also continued after the start of study treatment (Day 1) will be considered both as Prior and Concomitant.

Prior or concomitant medications and significant non-drug therapies will be listed and summarized in separate tabulations based on the latest version of the coding dictionary. Medications will be presented in alphabetic order, according to the Anatomical Therapeutic Chemical (ATC) classification system and by preferred term (PT). Tables will show the number and percentage of participants receiving at least one drug of a particular PT and at least one drug in a particular ATC class.

2.5 Analysis supporting primary objective

The primary endpoint analysis will be based on PK population.

2.5.1 Primary endpoint(s)/Primary estimand(s)

The primary endpoint is all TIN816 concentrations in serum PK parameters, including C_{max} , T_{max} , $T_{1/2}$, Cl , V_z , AUC_{last} and AUC_{inf} , and other relevant PK parameters (data permitting) (Table 2-1). It will be summarized descriptively for participants with at least one dose of study treatment.

There is no inferential analysis to be performed.

TIN816 serum concentration data will be listed by treatment, participant and visit/sampling time point. Descriptive summary statistics of TIN816 serum concentration data will be provided by treatment, and visit/sampling time point, including the frequency of concentrations below the LLOQ and reported as zero.

Summary statistics will include mean (arithmetic and geometric), standard deviation (SD), CV (arithmetic and geometric), median, minimum and maximum. An exception to this is T_{max} where median, minimum, and maximum will be presented. PK data will also be represented graphically (including spaghetti plots, and mean plots with SD) by treatment arm, participant and visit. Overlaying individual serum concentration-time profiles will be generated by treatment arm participant and visit/sampling time point.

Drug concentrations below LLOQ will be treated as missing for the calculation of the geometric means and geometric CV%, and as zero for all other calculations including calculation of PK parameters. Pharmacokinetic parameters will be calculated as described in CTIN816B12201 Protocol and will be listed by treatment and participant and summarized by treatment with descriptive statistics as listed below.

The pharmacokinetic parameters listed in the table below will be determined from the serum concentration time data using the actual recorded sampling times and non-compartmental method(s) with Phoenix WinNonlin (Version 6.4 or higher). Other relevant PK parameters may be added (data permitting).

Table 2-1 Pharmacokinetic parameters from Non-compartmental analysis

PK parameter	Definition
AUC_{last}	The area under the curve (AUC) from time zero to the last measurable concentration sampling time (T_{last}) (mass \times time \times volume-1)
AUC_{inf}	The AUC from time zero extrapolated to infinity (mass \times time \times volume-1)
AUC_{inf} / D	The AUC from time zero to infinity (mass \times time \times volume-1), normalized by actual dose (mg/kg)
AUC_{0-14d}	The AUC from time zero to 14 days post-dose (mass \times time \times volume-1)
C_{max}	The maximum (peak) observed serum drug concentration after single dose administration (mass \times volume-1)
C_{max} / D	The maximum (peak) observed serum drug concentration after single dose administration (mass \times volume-1), normalized by actual dose (mg/kg)
T_{max}	The time to reach maximum (peak) serum drug concentration after single dose administration (time)
$T_{1/2}$	The elimination half-life associated with the terminal slope (λ_z) of a semi logarithmic concentration-time curve (time)
CL	The total body clearance of drug from the serum (volume \times time-1)
V_z	The apparent volume of distribution during terminal phase (associated with λ_z) (volume)
V_{ss}	Estimate of the volume of distribution at steady state based on the last observed concentration (volume)

Urine PK concentration will be provided as appropriate and a renal clearance (CL_r) may be determined if data permit. In case a renal clearance is calculated, that parameter should be included in the tabulated statistical PK parameter output mentioned above. At least urine PK concentrations will be summarized as descriptive summary statistics, as done with serum PK concentrations.

